## 4.0 OVERVIEW OF STUDY DESIGN/INTERVENTION

### 4.1 Design

This is a prospective, single site phase II randomized trial examining the systemic efficacy (primary objective), clinical efficacy, safety, quality of life effects, duration of response, time to response, progression-free and overall survival (secondary objectives) of patients of Talimogene Laherparepvec with or without radiotherapy in patients with cutaneous metastases from melanoma, Merkel cell carcinoma, or other solid tumor malignancies.

### 4.2 Intervention

Patients with cutaneous metastases from melanoma, Merkel cell carcinoma or other solid tumor malignancy will be screened for eligibility. If a patient is found to have anything other than cutaneous metastases from melanoma, Merkel cell carcinoma or other solid tumor malignancy, appropriate clinical management will be undertaken.

If eligible, patients will undergo baseline PET/CT imaging, quality of life assessment, followed by intralesional Talimogene Laherparepvec with or without radiotherapy.

Talimogene Laherparepvec will be administered at weeks 0, 3, 5, 7, 9, 11, 13 and 15. The first dose of Talimogene Laherparepvec will be  $10^6$  plaque forming units (PFU)/mL, followed three weeks later by a dose of  $10^8$  pfu/mL. Up to 4 mL will be injected at each treatment. Metastases will be injected, beginning with the largest tumor first, with volumes indicated below, until a maximum of 4 mL has been used.

Tumor size (longest dimension)	Talimogene Laherparepvec (TVEC) injection volume	Dose concentration
>5 cm	$\leq 4$ mL	$10^6$ PFU/mL at week 0, $10^8$ PFU/mL thereafter
2.6-5 cm	$\leq 2$ mL	$10^6$ PFU/mL at week 0, $10^8$ PFU/mL thereafter
1.6-2.5 cm	$\leq 1$ mL	$10^6$ PFU/mL at week 0, $10^8$ PFU/mL thereafter
0.6-1.5 cm	$\leq 0.5$ mL	$10^6$ PFU/mL at week 0, $10^8$ PFU/mL thereafter
$\leq 0.5$ cm	$\leq 0.1$ mL	$10^6$ PFU/mL at week 0, $10^8$ PFU/mL thereafter

Table 1. TALIMOGENE LAHERPAREPVEC injection volume and concentration based on tumor size.

Patients randomized to Arm A will receive 3 radiotherapy treatments (one treatment every 3-6 days) during weeks 3 and 4. The first treatment will occur 6 (+/- 2) hours after the Talimogene Laherparepvec administration at week 3.

Patients randomized to Arm B will receive Talimogene Laherparepvec alone, as described above, without radiotherapy.

Patients will undergo disease re-evaluation with PET/CT and quality of life assessment at week 16.

Patients with potential for clinical benefit may continue Talimogene Laherparepvec every 2 weeks, after week 15, for up to 24 weeks. This will be determined by the treating clinician.

## **5.0 THERAPEUTIC/DIAGNOSTIC AGENTS**

Please see Investigational Product Information – Talimogene Laherparepvec (AMG 678). The agent is under review by the FDA for use in patients with melanoma and will be used under a cross-referenced IND for use in other diseases.

External beam radiation therapy is a standard, non-investigational treatment for cutaneous metastasis.

## **6.0 CRITERIA FOR SUBJECT ELIGIBILITY**

### **6.1 Subject Inclusion Criteria**

- Man or woman  $\geq$  18 years old
- Life expectancy  $>$  4 months
- Histopathologically confirmed melanoma, Merkel cell carcinoma or other solid tumor malignancy
- Cutaneous, subcutaneous soft tissue, or superficial lymphatic metastasis not suitable for surgical resection
- Eastern Cooperative Oncology Group (ECOG) performance status 0 to 2
- Cutaneous, subcutaneous soft tissue, or superficial lymphatic metastasis that is amenable to injection and irradiation and  $>$  10 mm in longest dimension
  - Cutaneous metastasis in a region of previous radiation therapy is amenable to radiation therapy as part of this protocol if at least 6 months has elapsed since prior radiotherapy and the dose of radiotherapy previously administered did not exceed an equivalent dose of 60 Gy in 2 Gy equivalent fractions at the skin surface (using linear-quadratic modeling with alpha/beta=11.5)
- Metastasis that is  $>$  10 mm in longest dimension or exhibits radiotracer uptake consistent with metastasis on PET/CT
- Adequate coagulation function (platelet count  $>$ 50 k/mcL, international normalized ratio of  $<$  1.5)
- Resolution or stabilization of clinically significant adverse events from prior therapy
- Able to provide valid written informed consent

### **6.2 Subject Exclusion Criteria**

- Active herpetic skin lesions or prior complications of HSV-1 infection (such as herpetic keratitis, herpetic encephalitis)
- Receipt of a therapeutic anticoagulant
- Receipt of live vaccine within 28 days of planned first dose of TVEC

- Receipt of another cancer therapy (targeted therapy, chemotherapy, investigational therapy, immunotherapy, radiotherapy or surgery) which is yielding an overall response (by response criteria in this study)
  - Patients with stable or progressing disease (as determined by at least 2 consecutive assessments at 6-week interval) can continue to receive the same therapy during treatment as part of this protocol
- History of symptomatic autoimmune disease (such as lupus, scleroderma, Crohn's disease, ulcerative colitis) requiring systemic treatment (for example corticosteroids or immunosuppressants); replacement therapy (for example, thyroxine, insulin) is not considered a systemic treatment
- History of high grade (CTCAE  $\geq$  Grade 3) immune mediated adverse event from prior cancer immunotherapy
- History of CTCAE  $\geq$  Grade 2 immune mediated endocrinopathy from prior cancer immunotherapy
- Intermittent or chronic use of oral or intravenous antiherpetic drug (such as acyclovir)
- Active or chronic hepatitis B or C infection
  - Previously infected with evidence of immunity and no evidence of active hepatitis is not an exclusion criterion
- Known human immunodeficiency virus (HIV) infection
- Known leukemia or lymphoma
- Common variable immunodeficiency
- Patients requiring chronic high dose immunosuppressants including steroids (prednisone daily equivalent of  $\geq$  10 mg)
- Known severe congenital or acquired cellular or humoral immunodeficient or immunocompromised patients (as noted in Investigators Brochure and Developmental Core Safety Information)
- High likelihood of protocol non-compliance (in opinion of investigator)
- Woman of childbearing potential unwilling to use effective contraception during protocol treatment and for 3 months after last dose of Talimogene Laherparepvec
- Woman of childbearing potential that is pregnant or breast-feeding, or planning to become pregnant or breast-feed during protocol treatment and for 3 months after last dose of Talimogene Laherparepvec

## 7.0 RECRUITMENT PLAN

Investigators and their research teams will serve as the primary recruiters for this study.

Potential research subjects will be identified by a member of the patient's treatment team, the protocol investigator, or the research team. If the investigator is a member of the treatment team, s/he will screen the patient's records for suitable research study criteria and discuss the study and the potential for enrolling in the research study. Potential subjects contacted by their treating physician will be referred to the investigator/research staff of the study. Women and minorities will be identified in this same manner.

During the initial contact between the investigator/research staff and the patient, the patient may be asked to provide certain health information that is necessary to the recruitment and enrollment process. The investigator/research staff may also review portions of the patients

medical records at MSKCC to further assess eligibility. They will use the information provided by the patient and/or medical record to confirm that the patient is eligible and to contact the patient regarding study enrollment. If the patient is ineligible for enrollment in the research study, the research staff will destroy all information collected on the patient during the initial conversation and medical records review, except for any information that must be maintained for screening log purposes.

In most cases, the initial contact with the prospective subject will be by a member of the treatment team, investigator or research staff working in consultation with the treatment team. The recruitment process outlined presents no more than minimal risk to the privacy of the patients who are screened and minimal PHI will be maintained as part of the screening log. For these reasons, we seek a (partial) limited waiver of authorization for purposes of (1) (2) handling of PHI contained within those records and provided by potential subjects; and (3) maintaining information in a screening log of patients approached (if applicable).

This limited waiver will apply only to MSKCC for the purpose of maintaining screening logs. The study will not be advertised. Subjects will not be reimbursed for participation.

We plan to accrue 18 - 34 patients at our center over 2 – 3 years.

## **8.0 PRETREATMENT EVALUATION**

The following tests and procedures are required prior to protocol registration. These procedures are standard of care.

Within 4 weeks prior to registration

- Physical examination
- ECOG performance status
- Vital signs (weight, heart rate, blood pressure, respiratory rate, oxygen saturation) will be assessed in clinic
- Complete blood count (CBC)
- Comprehensive metabolic profile (CMP)
- Hepatitis B and C panels (Hepatitis B Surface Antigen, Hepatitis B Core Antibody (total), Hepatitis B Surface Antibody, Hepatitis C Antibody), and possible additional testing, depending on serological testing
- Prothrombin and activated partial thromboplastin time test (PT&APTT)
- Clinical review of the MSK histopathology report confirming cancer
- Quality of life assessment (Skindex -16, Appendix B) will be completed by subjects
- Pregnancy test for women of childbearing potential (by either blood or urine)
- Digital photography will be performed to document the location and size of cutaneous metastases.
- PET/CT (IV or oral contrast is not required, but is permissible if clinically indicated.)

## **9.0 TREATMENT/INTERVENTION PLAN**

### **Study Assessments and Procedures**

#### **During Treatment**

Weeks 0, 3, 5, 7, 11 and 15 ( $\pm$  1 week)

- Physical examination
- ECOG performance status
- Vital signs (weight, heart rate, blood pressure, respiratory rate, oxygen saturation) will be assessed in clinic
- Complete blood count (CBC)
- Basic metabolic profile (BMP)
- Prothrombin and activated partial thromboplastin time test (PT&APTT)
- Pregnancy test for women of childbearing potential, by blood or urine (at weeks 3, 7, 11 and 15 only)
- Research blood test
- Research skin tumor biopsy (at weeks 0, 7 and 15 only)

Weeks 0-15 ( $\pm$  1 week)

- Administration of Talimogene Laherparepvec (T-VEC)  
*\* Patients with potential for clinical benefit may continue TALIMOGENE LAHERPAREPVEC after week 15 every 2 weeks for up to 24 weeks (to be determined by treating clinician)*
- Radiation therapy for patients randomized into Arm A; first fraction given 6 (+/-2) hours after week 3 Talimogene Laherparepvec administration; 2nd and 3rd fraction given every 3-6 days over next 14 days
- Adverse event review (including NCI PRO-CTCAE v1.0, Appendix C)

## **End of Treatment**

Week 16 ( $\pm$  1 week) or when TVEC is discontinued prior to week 15

- Physical examination
- ECOG performance status
- Vital signs (weight, heart rate, blood pressure, respiratory rate, oxygen saturation) will be assessed in clinic
- Adverse event review (including NCI PRO-CTCAE v1.0, Appendix C)
- Complete blood count (CBC)
- Comprehensive metabolic profile (CMP)
- Prothrombin and activated partial thromboplastin time test (PT&APTT)
- Research blood test (If TVEC stopped before week 15)
- Pregnancy test for women of childbearing potential (by either blood or urine)
- Research skin tumor biopsy (If TVEC stopped before week 15)
- Quality of life assessment (Skindex-16, Appendix B) to be completed by subjects
- Digital photography
- PET/CT (IV or oral contrast is not required, but is permissible if clinically indicated.)

## **Follow-Up**

Week 20 ( $\pm$  1 week) or 4 weeks after last TVEC dose

- Adverse event review (including NCI PRO-CTCAE v1.0, Appendix C)

## **9.1 Oncolytic immunotherapy by Talimogene Laherparepvec (TALIMOGENE LAHERPAREPVEC) administration**

Intralesional administration of Talimogene Laherparepvec will be performed in a private room in the outpatient clinic area.

Intralesional therapy for cutaneous metastasis is a standard procedure, but Talimogene Laherparepvec is an investigational agent.

The selection of cutaneous metastasis for Talimogene Laherparepvec injection will be based on lesion size. Injections will begin with the largest metastasis, and then will proceed to the next largest metastasis, until all the cutaneous metastases have been injected, or the maximum volume of Talimogene Laherparepvec (4 mL) has been used for that treatment cycle. The injection of all of the cutaneous metastases is expected to take no more than 20 minutes.

Visceral metastases will not be injected with Talimogene Laherparepvec during the protocol therapy.

During the course of Talimogene Laherparepvec administration, patients will be clinically evaluated every 2-3 weeks (as indicated in section 10.0), for any symptoms or signs of toxicity. If a patient experiences a grade 2 or higher immune mediated adverse event, Talimogene Laherparepvec administration will be delayed until the adverse event is grade 1 or less in severity. Non-immune related adverse events grade 3 or greater will also lead to a delay in Talimogene Laherparepvec administration, until they have resolved to grade 1 or less. In the event of a dose limiting toxicity, as described in section 11.1.3, Talimogene Laherparepvec administration will be discontinued indefinitely.

The first dose of radiation will be delivered 6 (+/- 2) hours after the second dose of Talimogene Laherparepvec. Preclinical studies have demonstrated this sequence of therapy and interval of time is necessary to yield synergistic effects of oncolytic immunotherapy and radiotherapy. The subsequent two doses of radiation therapy will occur every 3-6 days, over no more than 14 days.

During the course of radiation therapy patients will be clinically evaluated at least once a week, for any symptoms or signs of toxicity.

### 9.3 Cutaneous metastasis biopsy

Punch biopsy will be obtained for immunologic correlative analyses. Local anesthesia will be provided by intradermal injection of lidocaine 1% mixed with epinephrine at 1:100,000 by a 30 gauge needle. After allowing 5 minutes for adequate anesthesia, a 3 mm punch biopsy will be obtained. The biopsy site will be closed with cuticular sutures or steri-strips. Patients will be instructed to keep the biopsy site clean after the procedure. This procedure will be done as an outpatient. The biopsy is expected to take no longer than 15 minutes and will be performed on the day of (but prior to first dose) of oncolytic immunotherapy. The biopsy will be repeated around 7 and 15 weeks after the first dose, at the site of the prior biopsy, and at up to two other sites (if present): (1) the site of another cutaneous metastasis that was not injected or irradiated (if present), (2) the site of another cutaneous metastasis that was injected but not irradiated (if present).

## 10.0 EVALUATION DURING TREATMENT/INTERVENTION

Study Timeline	Pre-Treatment	Treatment									End of Treatment 	Follow-Up 
		0 (1)	3 (1)	5 (1)	7 (1) 	9 (1)	11 (1)	13 (1)	15 (1)	16 (1)		
Week (+/-)	-4 to 0											
Assessments												
Pathology Review	X											
PET/CT (with or without contrast)	X									X		
Quality of life questionnaires	X									X		
Digital photography	X									X		
Adverse event		X	X	X	X	X	X	X	X	X		X

review 											
ECOG performance status	X	X	X	X	X		X		X	X	
Vital signs (weight, heart rate, blood pressure, respiratory rate, oxygen saturation)	X	X	X	X	X		X		X	X	
Physical exam	X	X	X	X	X		X		X	X	
Complete medical history	X										
Hepatitis B Surface Antigen, Hepatitis B Core Antibody (total), hepatitis B surface Antibody, Hepatitis C Antibody 	X										
Comprehensive metabolic profile	X									X	
Basic metabolic profile		X	X	X	X		X		X		
Complete blood count	X	X	X	X	X		X		X		
PT&APTT	X	X	X	X	X		X		X		
Pregnancy testing (blood or urine); WOCBP only	X 		X		X		X		X		
Research blood test 		X	X	X	X		X		X		
Research skin punch biopsy 		X			X				X		
Treatment											
TALIMOGENE LAHERPAREPVEC		X	X	X	X	X	X	X	X†		
Radiation therapy			X*								

†Patients with potential for clinical benefit may continue TALIMOGENE LAHERPAREPVEC after week 15 every 2 weeks for up to 24 weeks (as determined by treating clinician)

\*Only for Arm A; first fraction given 6 (+/- 2) hours after week 3 TALIMOGENE LAHERPAREPVEC administration; 2nd and 3rd fraction given every 3-6 days over no more than 14 days

Including Appendix C, "NCI PRO-CTCAE v1.0"

Within 2 weeks of starting Talimogene Laherparepvec treatment

 Research bloods will be 3 tubes (3 CPT) at each time point; stored at immune monitoring core facility for up to 1 year after completion of study

One lavender top (EDTA) tube of blood will be drawn on the same day as the research skin punch biopsy; window for biopsy will be +/- 3 weeks

Additional testing to evaluate for hepatitis maybe required depending on the serological results

For patients that discontinue TVEC before week 16, the End of Treatment visit occurs after last dose of TVEC

Follow-Up at week 20 or 4 weeks after last TVEC dose

## 11.0 TOXICITIES/SIDE EFFECTS

The study will use the Common Terminology Criteria for Adverse Events (CTCAE) version 4.0 for assessing toxicity related to oncolytic immunotherapy and radiotherapy.

Overall, toxicities grade 2-5 will be identified, graded and scored using “Common Toxicity Criteria for Adverse Events, version 4.0, grading criteria and definitions”.

### 11.1 TALIMOGENE LAHERPAREPVEC

Side effects of Talimogene Laherparepvec for cutaneous metastasis are listed below. Also see Investigators Brochure, Developmental Core Safety Information, Toxicity Management Guidelines for studies with Talimogene Laherparepvec [AMG 678] and Core Informed Consent Form Risks and Discomforts Section.

#### 11.1.1.0 Important Identified Risks

- Disseminated herpetic infection in severely immunocompromised individuals (those with any severe congenital or acquired cellular and/or humoral immune deficiency)
- Accidental exposure of healthcare providers (HCPs) to talimogene laherparepvec
- Cellulitis at site of injection

#### 11.1.1.1 Important Potential Risks

- Disseminated herpetic infection in immunocompromised patients (such as those with HIV/AIDS, leukemia, lymphoma, common variable immunodeficiency, or those who require high dose steroids or other immunosuppressive agents)
- Symptomatic talimogene laherparepvec infection in non-tumor tissue in treated patients
- Transmission of talimogene laherparepvec from patient to close contacts or HCPs via direct contact with injected lesions or body fluids resulting in symptomatic infection (primary or reactivation)
- Symptomatic herpetic infection due to latency and reactivation of talimogene laherparepvec or wild type HSV-1
- Immune-mediated adverse events
- Plasmacytoma at the injection site
- Impaired wound healing at the injection site
- Talimogene laherparepvec mediated anti GM-CSF antibody response

#### 11.1.2.0 Adverse Drug Reactions (ADRs)

Adverse drug reactions observed in talimogene laherparepvec clinical trials are listed below in Table 2. Consult the current Investigator’s Brochure for the full information on ADRs.

System Organ Class Preferred Term	CIOMS Frequency
	Very Common: ≥10% Common: 1%-<10% Uncommon: <1%
General disorders and administration site conditions	
Fatigue	Very Common
Chills	Very Common
Pyrexia	Very Common
Influenza like illness	Very Common
Malaise	Common
Axillary pain	Common
Injection site reactions*	Very Common
Gastrointestinal disorders	
Nausea	Very Common
Vomiting	Very Common
Diarrhea	Very Common
Constipation	Very Common
Abdominal pain	Common
Abdominal discomfort	Common
Musculoskeletal and connective tissue disorders	
Myalgia	Very Common
Arthralgia	Very Common
Pain in extremity	Very Common
Groin pain	Common
Skin and subcutaneous tissue disorders	
Vitiligo	Common
Rash	Common
Dermatitis	Common
Infections and infestations	
Cellulitis	Common
Oral herpes	Common
Incision site infection	Uncommon
Nervous system disorders	
Headache	Very Common
Dizziness	Common
Eye disorders	
Herpetic keratitis	Uncommon
Respiratory, thoracic and mediastinal disorders	
Oropharyngeal pain	Common
Obstructive airway disorder	Uncommon
Metabolism and nutrition disorders	
Dehydration	Common
Injury, poisoning and procedural complications	
Contusion	Common
Procedural pain	Common
Wound complication	Common
Wound secretion	Common
Neoplasms benign, malignant and unspecified (incl cysts and polyps)	

System Organ Class Preferred Term	CIOMS Frequency
	Very Common: ≥10%
	Common: 1%-<10%
Tumor pain	Common
Infected neoplasm	Common
Plasmacytoma at the injection site	Uncommon
Investigations	
Weight decreased	Common
Vascular disorders	
Deep vein thrombosis	Common
Flushing	Common
Blood and lymphatic system disorders	
Anemia	Common
Immune system disorders	
Worsening psoriasis	Uncommon
Pneumonitis	Uncommon
Glomerulonephritis	Uncommon
Vasculitis	Uncommon

\* Injection site reactions include: very common term of injection site pain, common terms of injection site erythema, injection site hemorrhage, injection site swelling, injection site reaction, injection site inflammation, secretion discharge, injection site discharge, uncommon term of injection site warmth.

Table 2. ADRs Observed in Talimogene Laherparepvec Clinical Trials

#### 11.1.3.0 Dose Limiting Toxicities (DLTs)

Dose limiting toxicities (DLTs) are defined below.

#### 11.1.3.1 Definitions of Dose Limiting Toxicity

Toxicity should be evaluated according to CTCAE version 4.0, and should only include events assessed as related to talimogene laherparepvec during treatment and up to 30 days after the last talimogene laherparepvec injection.

The following herpetic events should be considered as DLTs:

- Serious herpetic events such as herpetic encephalitis, encephalomyelitis or disseminated herpetic infection
- Any herpetic events confirmed due to talimogene laherparepvec that require treatment with acyclovir or similar anti-viral agent. Talimogene laherparepvec treatment should be suspended if treatment is required with systemic acyclovir or other anti-virals. If ongoing anti-viral treatment is required, talimogene laherparepvec treatment should be permanently discontinued

Consider also including the following as DLTs:

- Grade 3 or greater immune-mediated adverse events
- Any grade plasmacytoma at or near the injection site or evidence of impaired wound healing at the injection site
- Grade 3 or greater allergic reactions considered at least possibly related to talimogene laherparepvec
- Grade 4 non-hematologic toxicity
- Grade 3 non-hematologic toxicity lasting > 3 days despite optimal supportive care
  - Grade 3 fatigue will not be classified as DLT, irrespective of duration
- Any grade 3 or higher non-hematologic laboratory value if the abnormality:
  - fails to respond to medical intervention, or
  - leads to hospitalization, or
  - persists for > 1 week unless deemed not clinically important per both investigator and sponsor
- Grade 3 or 4 febrile neutropenia
- Grade 4 thrombocytopenia associated with a bleeding event deemed at least possibly related to talimogene laherparepvec and requiring intervention
- Any other intolerable toxicity leading to permanent discontinuation of talimogene laherparepvec
- Grade 5 toxicity (ie. Death)

If an unexpected DLT deemed at least possibly related to talimogene laherparepvec occurs, talimogene laherparepvec administration should be delayed until the DLT has resolved to at least CTCAE (v. 4.0) Grade 1.

If talimogene laherparepvec dosing is delayed by more than 6 weeks from the date of the planned dose due to the occurrence of an adverse event that is considered related to talimogene laherparepvec, the subject must be permanently taken off talimogene laherparepvec treatment.

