### **11.1.4**

#### **Talimogene Laherparepvec Dosage Adjustments, Delays, Rules for Withholding or Restarting, Permanent Discontinuation**

If talimogene laherparepvec treatment was delayed by > 2 weeks, that dose will be deemed to have been missed and the subject will proceed to the next scheduled treatment visit. Dose reductions of talimogene laherparepvec is not permitted, other than a reduction in the volume injected due to a disease response.

If a subject experiences any of the following treatment-related toxicities, talimogene laherparepvec administration should be delayed until the toxicity has resolved to at least CTCAR grade 1 or baseline:

- Grade 2 or greater immune-mediated adverse events, with the exception of vitiligo
- Grade 2 or greater allergic reactions
- Any other grade 3 or greater hematologic or non-hematologic toxicity

Subjects who are receiving talimogene laherparepvec may not receive systemic antiherpetic drugs (eg, acyclovir, valacyclovir, famciclovir), but may receive a topically administered antiherpetic drug more than 20 cm from a talimogene laherparepvec injection site. Dosing should be permanently discontinued if, in the opinion of the investigator, the subject develops clinical evidence of any systemic herpes infection (such as encephalitis or disseminated infection). If the subject requires corticosteroid dosing of > 10 mg prednisone daily (or equivalent) for related toxicities, talimogene laherparepvec dosing must be withheld until the corticosteroid dose has decreased to  $\leq$  10 mg prednisone daily (or equivalent).

Talimogene laherparepvec treatment should be continued based on the potential benefit/risk assessment of the subject. If talimogene laherparepvec dosing is delayed by more than 4 weeks from the date of the planned dose (ie, approximately 6 weeks or 7 weeks depending whether the patient is receiving Q2W or Q3W dosing from the previous dose) due to the occurrence of an adverse event that is considered related to talimogene laherparepvec, the subject must be permanently withdrawn from talimogene laherparepvec treatment.

Talimogene laherparepvec is to be permanently discontinued for subjects meeting any of the following criteria:

- The subject, for any reason, requires treatment with another anticancer therapeutic agent for treatment of the study disease. In this case, discontinuation from the treatment occurs immediately upon introduction of the new agent.
- Confirmed PD

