- A grade 2 or greater immune-mediated adverse event (with the exception of vitiligo) or allergic reactions attributed to talimogene laherparepvec that would require a dose delay of greater than 4 weeks from the date of the planned dose (ie, approximately 6 weeks from the previous dose).  
Note: immune-mediated glomerulonephritis, vasculitis, and pneumonitis and exacerbation of psoriasis have been observed in subjects receiving

talimogene laherparepvec in clinical trials. Most of these subjects had a history of other autoimmune disease and/or prior treatment with agents that offered plausible alternative etiologies, however, immune-mediated adverse events can potentially involve any organ system

- Any other talimogene laherparepvec-related non-hematologic or hematologic toxicities grade 3 or greater occur that, in the opinion of the investigator, would require a dose delay of greater than 4 weeks from the date of the planned dose (ie, approximately 6 weeks from the previous dose)
- The subject develops clinical evidence of any systemic herpes infection (such as encephalitis or disseminated infection)
- A female subject becomes pregnant or fails to use acceptable method(s) of affective contraception (for those subjects who are able to conceive)
- Concurrent medical illness that, in the judgment of the investigator, would make continued treatment with talimogene laherparepvec dangerous for the subject

For additional information related to special warnings and precautions for the use of talimogene laherparepvec, please refer to the latest version of the Investigator's Brochure.

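### Section 11.1.3.1 allows a related dosing delay of 6 weeks before a mandatory permanent stop where section 11.1.4 allows 4, and sections 9.1, 11.1.3.1 and 11.1.4 disagree on what follows a dose limiting toxicity

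*Combined protocol and SAP*

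**What the plan says.** **Length of delay.** Section 11.1.3.1 of the combined protocol and SAP closes with a rule for delays caused by an adverse event judged related to the drug: "If talimogene laherparepvec dosing is delayed by more than 6 weeks from the date of the planned dose", then "the subject must be permanently taken off talimogene laherparepvec treatment". Section 11.1.4, the section on dose adjustments, delays and permanent discontinuation, has a rule for the same situation: "If talimogene laherparepvec dosing is delayed by more than 4 weeks from the date of the planned dose", then "the subject must be permanently withdrawn from talimogene laherparepvec treatment". It translates its limit into time since the last injection: "approximately 6 weeks or 7 weeks depending whether the patient is receiving Q2W or Q3W dosing from the previous dose". Its list of permanent-discontinuation criteria repeats the 4-week figure twice. One criterion covers immune-mediated events of grade 2 or more (vitiligo excepted) and "allergic reactions attributed to talimogene laherparepvec that would require a dose delay of greater than 4 weeks from the date of the planned dose". The other covers other related toxicities of grade 3 or more that, "in the opinion of the investigator, would require a dose delay of greater than 4 weeks from the date of the planned dose".

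**Consequence of a DLT.** Section 9.1 makes no exception: "In the event of a dose limiting toxicity, as described in section 11.1.3, Talimogene Laherparepvec administration will be discontinued indefinitely". Section 11.1.3.1 is milder in two cases. A herpetic event confirmed as due to the drug and needing antivirals leads to suspension, which becomes permanent only if antiviral treatment has to continue. An unexpected DLT at least possibly related to the drug leads to a delay until grade 1. Section 11.1.4 separately delays dosing until grade 1 or baseline for three groups of treatment-related toxicity: immune-mediated events of grade 2 or more (vitiligo excepted), allergic reactions of grade 2 or more, and any other toxicity of grade 3 or more.

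**The concern.** These are patient safety rules, and the two delay rules are both worded as obligations. They share the trigger, the reference date and the consequence; only the number differs. A treating clinician who consults 11.1.3.1 alone, when a patient's related event resolves 5 weeks after the missed dose date, finds nothing that requires a stop. Section 11.1.4 required withdrawal a week earlier.

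The DLT rules raise a similar problem. The same event can end treatment under 9.1 and merely interrupt it under 11.1.3.1 or 11.1.4. Section 4.1 describes a single-site trial, so the risk is not that sites diverge. It is that one team handles similar patients differently according to which section it reads.

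**Working it through.** No power or error-rate calculation applies. The check compares the rules and converts the delay limits.

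**1. Reproduce the plan's own conversion.** Inputs: a limit of 4 weeks from the planned dose (11.1.4), and dosing at weeks 0, 3, 5, 7, 9, 11, 13 and 15 (section 4.2), which gives a first interval of 3 weeks and later intervals of 2 weeks.

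Time since previous dose = delay limit + dosing interval.

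- 2-week interval: 4 + 2 = 6 weeks
- 3-week interval: 4 + 3 = 7 weeks

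Both match the figures in 11.1.4, so its 4-week rule is internally consistent.

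**2. Apply the same conversion to 11.1.3.1.**

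| Rule | From planned dose | From previous dose, 2-week interval | From previous dose, 3-week interval |
|---|---|---|---|
| 11.1.4 | more than 4 weeks | more than 6 weeks | more than 7 weeks |
| 11.1.3.1 | more than 6 weeks | 6 + 2: more than 8 weeks | 6 + 3: more than 9 weeks |

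The disputed window is 6 − 4 = 2 weeks: related delays of more than 4 and up to 6 weeks. There 11.1.4 requires permanent withdrawal and 11.1.3.1 does not yet require it.

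**3. Could the two figures mean the same thing?** They would coincide if the 6 weeks ran from the previous dose at 2-week dosing. But 11.1.3.1 counts from the planned dose, as 11.1.4 does. A slip in the reference date is a plausible origin for the 6, but the documents do not say so.

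**4. Compare the DLT consequences.** Section 11.1.3.1 lists 2 herpetic items, plus 10 others that it only suggests considering.

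| DLT type | 9.1 | 11.1.3.1 | 11.1.4 |
|---|---|---|---|
| Systemic herpetic infection | stop | no separate lesser rule for systemic infection | permanent stop |
| Confirmed herpetic event, antiviral course not ongoing | stop | suspend | no systemic antivirals while on drug |
| Unexpected, at least possibly related | stop | delay to grade 1 | delay to grade 1 or baseline if in its three groups |
| Expected, non-herpetic | stop | no resume rule | delay to grade 1 or baseline if in its three groups |

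Systemic herpetic infection is not in conflict between 9.1 and 11.1.4. The next two rows are in conflict between 9.1 and 11.1.3.1. The last row conflicts with 11.1.4 wherever its three groups apply.

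**5. How far does 11.1.4 reach into the 10 suggested items?** Seven fall within its delay rule:

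- immune-mediated events of grade 3 or more
- allergic reactions of grade 3 or more
- grade 4 non-hematologic toxicity
- prolonged grade 3 non-hematologic toxicity
- non-hematologic laboratory values of grade 3 or more
- febrile neutropenia
- grade 4 thrombocytopenia with bleeding

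Plasmacytoma or impaired wound healing falls within it only at grade 3 or more. Death, and intolerable toxicity that already leads to permanent discontinuation, raise no question of resuming. So 7 + 1 + 2 = 10, and most items are affected, expected or not, if they are adopted as DLTs.

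**The case against.** The strongest reply on the delay limit is that the two rules can both be obeyed. Section 11.1.3.1 makes removal mandatory beyond 6 weeks; it does not say that dosing may resume between 4 and 6. A team following the whole protocol stops at 4 weeks, and 11.1.4 is the dedicated section. This stands. A reader might infer that 11.1.3.1 authorises re-dosing in the window, or that the team faces two incompatible orders. Neither follows from the text. What remains is a looser figure that serves no purpose and can mislead.

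A second reply is that re-dosing already requires the event to have resolved to grade 1 (or baseline, in 11.1.4), and that 11.1.4 adds a benefit/risk assessment. This also stands. A reader might infer that patients would be harmed by a dose at 5 weeks rather than 4; the documents give no evidence on that.

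A third is that 11.1.4 treats a dose delayed by more than 2 weeks as missed, so the clock might restart. That would leave 11.1.4's own 4-week limit unreachable, and its conversion to 6 or 7 weeks since the previous dose shows that the clock runs on. It is fair, though, that the dosing calendar adds little to the argument. A dose planned for week 3 and delayed 6 weeks lands on the week 9 visit, exactly at the edge of the window, and the ±1 week allowance can move it out.

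On DLTs, indefinite discontinuation in 9.1 might be read as an open-ended hold, which would soften the conflict. But the same paragraph of 9.1 speaks of delay until resolution for lesser events, so it appears to distinguish the two actions.

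**Conclusion.** The 6-week limit in 11.1.3.1 is wrong as written. It exceeds the limit in 11.1.4 by 2 weeks, for the same trigger, reference date and consequence. This rests on the current text alone and needs no assumption about how the mismatch arose.

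The disagreement over DLTs is real but secondary, because its resolution is a clinical choice. Its reach depends on which of the 10 suggested items are adopted, and on reading 9.1 as a permanent stop. A reader who compares 9.1 with 11.1.3.1 only might infer that the conflict is confined to two groups (herpetic events needing a limited antiviral course, and unexpected related DLTs) and that 9.1 governs every expected non-herpetic DLT. Section 11.1.4 does not support that, since its delay rule applies whether or not the event was expected.

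The number of patients affected cannot be estimated from the documents. A reader might also infer that the primary analysis is compromised. The stage sizes, cut-offs and error rates in section 14.0 do not depend on these rules. A stop before week 15 does bring forward the end-of-treatment visit and its PET/CT (section 9.0), but nothing in the documents allows an effect on the result to be quantified.

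**What to change.** In 11.1.3.1, change 6 weeks to 4 weeks so that it matches 11.1.4. This is a wording change.

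Then align 9.1, 11.1.3.1 and 11.1.4 so that each DLT type has one stated consequence. Amending 9.1 and 11.1.3.1 alone would leave the conflict with 11.1.4 in place. The amended text should say which of the 10 suggested items count as DLTs, because 9.1 acts on that list. Which items to adopt, and whether each type stops or may resume, is for the clinical team and the drug supplier to decide.

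The cost is one protocol amendment with institutional review board approval (section 16.3.1). It adds no patients, procedures or analyses. The stop-or-resume decisions will affect the drug exposure of the patients concerned.
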